6.2.2 Forced Expiratory Volume in 1 second

FEV₁ is the volume of air that can be forcibly exhaled from the lungs in the first second, measured in liters by a spirometer. FEV₁ (L) will be reported in the study results.

6.2.3 Fractional Exhaled Nitric Oxide

A FeNO test measures the levels of nitric oxide during exhalation, measured in ppb. A FeNO test will be done by breathing into a tube attached to a handheld monitor.

6.2.4 Asthma Control Questionnaire

The ACQ is a questionnaire to measure the adequacy of asthma control and change in asthma control. The questionnaire has a multidimensional construct assessing symptoms (5 items, selfadministered, looking back at the past week), rescue bronchodilator use (1 item, selfadministered, looking back at the past week), and FEV₁ (1 item, completed by study staff). For each of the self-administered questions (items), scoring is done on a 7point scale, ranging between 0 (totally controlled) and 6 (extremely poorly controlled).

All the items in the questionnaire are equally weighted and so the overall score for each assessment is the mean of the responses to the 7 items. The overall score also ranges between 0 (totally controlled) and 6 (extremely poorly controlled) [4].

The aim is not to have any missing data on the questionnaire. If there is more than one missing value per completed questionnaire, the data for that questionnaire will not be used (ie, will be set to missing). The following interpolation method will be used to impute a missing value, in case of a single missing value other than Item 1 or Item 7 on the ACQ questionnaire (values from either previous or subsequent completions of the questionnaire for the same subject can be used to impute a missing value) – the method is explained by means of an example [4]:

For the following example data (note that in the example the previous visit is used to impute the missing value at Visit 2; as a rule the closest complete previous visit will be used to impute a missing value, and if no complete previous visit is available, the closest complete subsequent visit's data will be used to impute a missing value from an incomplete visit):

	Visit 1	Visit 2
Item 1	4	6
Item 2	3	5
Item 3	4	4
Item 4	5	6
Item 5	2	Missing
Item 6	4	3
Item 7	3	5

Total Visit 1 score for items answered on both visits: $4 + 3 + 4 + 5 + 4 + 3 = 23$ (A)

Total Visit 2 score for items answered on both visits: $6 + 5 + 4 + 6 + 3 + 5 = 29$ (B)

Item 5 (item for which there is missing value at Visit 2) score at Visit 1 = 2 (C)

Imputed Item 5 score at Visit 2: $\frac{B}{A} \times C = \frac{29}{23} \times 2 = 2.52$

After imputation of the missing value, the overall score for each of Visit 1 and Visit 2 therefore will be:

Visit 1: $\frac{(4+3+4+5+2+4+3)}{7} = 3.57$

Visit 2: $\frac{(6+5+4+6+2.52+3+5)}{7} = 4.50$

Imputed values will be flagged in subject listings.

The overall score will be derived as the mean of the responses to the 7 items on the completed questionnaire when there is no missing data for a questionnaire or when a single missing value (ie, other than Item 1 or Item 7) was imputed according to the method above (in this case, the imputed value is used when calculating the mean). In the case where the only missing result for the completed questionnaire is either Item 1 or Item 7, the overall score will be derived using the

responses of the 6 completed items on the questionnaire (ie, the denominator when calculating the mean is 6 in this case). If there is more than one missing value per completed questionnaire, an overall score is not calculated (ie, will be set to missing).

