6.2.5 Standardized Asthma Quality of Life Questionnaire for Ages 12 to 70 years

The AQLQ(S)+12 includes 32 questions (items) in 4 domains (symptoms, activity limitation, emotional function, and environmental stimuli) [5].

The questionnaire is selfadministered. Subjects will be asked to recall their experiences during the previous 2 weeks and score each of the questions on a 7point scale, where 7=not at all limited and 1=totally limited.

The 32 questions (items) are assigned as follows to the 4 domains:

Symptoms: Items 6, 8, 10, 12, 14, 16, 18, 20, 22, 24, 29, 30

Activity limitation: Items 1, 2, 3, 4, 5, 11, 19, 25, 28, 31, 32

Emotional function: Items 7, 13, 15, 21, 27

Environmental stimuli: Items 9, 17, 23, 26

Individual items are equally weighted. The overall score of the AQLQ(S)+12 will be derived as the average of the 32 items; thus, the overall score ranges from 1 ("total impairment") to 7 ("no impairment"). The domains are summarized in exactly the same way – each domain score will be derived as the average score of the items for the specific domain. Each domain score thus also ranges from 1 ("total impairment") to 7 ("no impairment").

The aim is not to have any missing data on the questionnaire. The data for a completed questionnaire will not be used (ie, will be set to missing) in the following cases:

- For calculation of overall score: if > 3 missing responses in total or > 1 missing response in any domain
- For calculation of symptom or activity limitation domain scores: if > 1 missing response in the domain, or
- For calculation of emotional function and environmental stimuli domain scores: if any missing response in the domain.

In case the number of missing values does not exceed the specifications listed above, imputation of missing values will be performed using the same method as described for the ACQ questionnaire in [Section 6.2.4](#) [5].

Imputed values will be flagged in subject listings.

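### The ACQ single-item imputation is not held to the 0-6 item scale, is undefined when the donor total is 0, and places no pre-dose limit on donors for the baseline questionnaire

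*SAP*

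**What the plan says.** SAP 6.2.4 states that "The overall score also ranges between 0 (totally controlled) and 6 (extremely poorly controlled", and gives the self-administered items the same range. The ratio imputation applies "in case of a single missing value other than Item 1 or Item 7 on the ACQ questionnaire". A is the "Total Visit 1 score for items answered on both visits", B is the "Total Visit 2 score for items answered on both visits", and C is the donor-visit score of the missing item; the imputed value is B/A x C. The first-choice donor is the nearest complete earlier visit. If there is none, "the closest complete subsequent visit's data will be used to impute a missing value". The method is attributed to the instrument manual (SAP reference 4), and imputed values are flagged in listings.

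A different rule applies to two items. "In the case where the only missing result for the completed questionnaire is either Item 1 or Item 7", the overall score is the mean of the six answered items. A questionnaire with more than one missing item gets no score.

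SAP 6.2.5 carries the ratio over to the AQLQ(S)+12, within that instrument's own limits on missing responses: "imputation of missing values will be performed using the same method as described for the ACQ questionnaire". Its items run from 1 to 7.

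SAP 9.2 defines baseline, unless otherwise specified, as the last assessment available before first dose. SAP 10.6.2 summarises ACQ and AQLQ(S)+12 descriptively, as observed values and change from baseline.

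**The concern.** A ratio of totals multiplied by an item score does not respect the item's scale. If the six common items rise between the donor visit and the incomplete visit, B/A exceeds 1, and a moderately high donor item can be pushed past 6. The design makes such rises plausible: salmeterol stops at Day 14, and fluticasone is halved at Day 28 and stopped at Day 42. A ratio above 1 is what the method intends when a subject worsens. The fault is only that the result is not confined to values the item can take.

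Two further cases are left open. If all six common items are 0 at the donor visit, the formula divides by zero and a programmer must invent a rule. If the Visit 2 questionnaire lacks one item and no earlier questionnaire is complete, the donor is a visit after first dose, so post-dose information enters a baseline item.

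At stake are individual ACQ and AQLQ(S)+12 scores, and through them the change-from-baseline summaries.

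**Working it through.** **Inputs.** Formula, item range and donor order: SAP 6.2.4. AQLQ(S)+12 range: SAP 6.2.5. ACQ entry threshold of at least 1.5 at Screening: Protocol 8.5 and 8.5.1. Assumption: Item 7 is also scored 0 to 6, as the equal weighting and the 0-6 overall range imply.

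**The SAP's own example.** A = 23, B = 29, C = 2. Imputed item = 29/23 x 2 = 2.52. Overall scores: Visit 1, 25/7 = 3.57; Visit 2, (29 + 2.52)/7 = 4.50. All as printed.

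**Range, ACQ.** Overall score = (B + B/A x C)/7.

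| A | B | C | Donor score (A + C)/7 | Imputed item | Overall as written | Overall, item capped at 6 |
|---|---|---|---|---|---|---|
| 6 | 18 | 3 | 1.29 | 9.0 | 27/7 = 3.86 | 24/7 = 3.43 |
| 12 | 24 | 4 | 2.29 | 8.0 | 32/7 = 4.57 | 30/7 = 4.29 |
| 5 | 36 | 6 | 1.57 | 43.2 | 79.2/7 = 11.31 | 42/7 = 6.00 |
| 1 | 36 | 6 | 1.00 | 216 | 252/7 = 36.0 | 42/7 = 6.00 |

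The last two rows are arithmetic limits, not expected cases. Row 3 is the limit when the donor is a complete Screening questionnaire that met the entry threshold: seven integer items averaging at least 1.5 sum to at least 11, so with C at most 6, A is at least 5. Row 2 is a moderate case whose donor also meets the threshold.

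**Truncation.** The true item lies between 0 and 6. Moving an imputed value from outside that interval to its nearer end always brings it closer to the true value, so a cap cannot increase the error of any imputed item.

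**A = 0.** This needs a complete donor with all six common items at 0. It cannot be an eligible Screening questionnaire (A at least 5, as above), but it can be a later, well-controlled visit.

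**Post-dose donor for baseline.** Two gaps must coincide: one of Items 2 to 6 missing at Visit 2, and no complete earlier questionnaire. The second is possible because a Screening form missing only Item 1 or Item 7 still yields a score but is not complete. What then enters is limited:
- Proportional response. Baseline items all 4, donor items all 2: 24/12 x 2 = 4. The treatment effect cancels.
- Item-specific response. Same baseline, six donor items at 2 but the missing item at 1: 24/12 x 1 = 2 instead of 4. The baseline score becomes 26/7 = 3.71 instead of 4.00, an error of 2/7 = 0.29.

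**AQLQ(S)+12, one item missing, 31 common items.**
- Above 7: common items go from 4 to 6 and C = 6, giving (31 x 6)/(31 x 4) x 6 = 9.
- Below 1: common items go from 4 to 2 and C = 1, giving (31 x 2)/(31 x 4) x 1 = 0.5.
- A is at least 31, so division by zero cannot occur.

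**The case against.** The defence has four good points.

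First, the method is cited to the instrument manuals, which cannot be consulted here and may contain bounds that the SAP does not repeat. That stands as a reason to keep the ratio. It does not settle the matter, because programming follows the SAP, and the SAP states no bound.

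Second, the first row of the table is steep: its donor score of 1.29 is below the entry threshold, so the donor cannot be the qualifying Screening questionnaire, and the six answered items triple. Row 2 does not depend on that. How often the scale is exceeded does depend on assumptions. In illustrative simulations of rounded 0-6 items, at most about 5% of imputed items exceeded 6 when the mean item rose by 0 to 0.5 between visits. With rises of 1 to 2 points the figure was roughly 4% to 28%, depending on the assumed item structure.

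Third, a reader might infer that baseline is built from post-dose data and that change from baseline is therefore biased. The documents do not support that. Six of the seven items are the subject's own baseline answers, B/A rescales the borrowed item to the baseline level, and Screening is the normal donor. Only an item-specific response leaves an error, with a weight of one seventh.

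Fourth, a reader might infer that the mean of the six answered items should replace the ratio altogether, since the SAP already uses it for Items 1 and 7. It is always in range and always defined, but it discards the subject's item profile and moves the SAP's own example from 4.50 to 29/6 = 4.83. Which method is more accurate depends on how stable item profiles are. Under assumed stable profiles (item SD 0.9, visit noise 0.5) the capped ratio had a root mean squared error of 0.92 to 1.07, against 1.10 to 1.13 for the item mean. Under noisy profiles (0.5 and 0.9) the item mean had 1.10 to 1.13, against 1.52 to 1.84 for the uncapped ratio. Both comparisons assumed a subject SD of 0.7, starting means of 2.0 to 2.5 and mean changes of 0 to 0.5. The documents give nothing on item stability, so they do not support the item mean as the better estimator in general.

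**Conclusion.** The concern holds as a gap in the written rule, of minor consequence. As specified, the ACQ imputation can return items outside the 0-6 range that the same section states, and it is undefined at A = 0. It also lets a post-dose visit supply the profile for one missing baseline item when no earlier questionnaire is complete. The AQLQ(S)+12 shares the range problem in both directions but not the division by zero.

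In the moderate examples the excess is 2 or 3 points on the item, and 0.29 (4.57 against 4.29) or 0.43 (3.86 against 3.43) on the ACQ overall score of that one questionnaire. Only questionnaires with a single gap in Items 2 to 6, or a permitted gap in the AQLQ(S)+12, are touched. The documents do not say how many that will be; few is a reasonable expectation, not a stated figure. Imputed values are flagged, the endpoints are descriptive and secondary, and the primary analysis uses neither score.

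**What to change.** Keep the ratio method and add three provisions to SAP 6.2.4, with a matching reference in 6.2.5:

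1. Truncate every imputed item to its scale: 0 to 6 for the ACQ, 1 to 7 for the AQLQ(S)+12.
2. When A = 0 (ACQ only), either score the mean of the six answered items or set the overall score to missing. Choose one before unblinding.
3. For a questionnaire completed before first dose, allow only pre-dose donors. If none is complete, use the mean of the answered items, as is already done when Item 1 or Item 7 is the only gap, or set the score to missing.

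The cost is SAP wording and a few lines of programming, with no change to data collection. The downside is a small addition to the manual's interpolation as the SAP cites it, which should be stated as such.

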6.2.5 Standardized Asthma Quality of Life Questionnaire for Ages 12 to 70 years

The AQLQ(S)+12 includes 32 questions (items) in 4 domains (symptoms, activity limitation, emotional function, and environmental stimuli) [5].

The questionnaire is selfadministered. Subjects will be asked to recall their experiences during the previous 2 weeks and score each of the questions on a 7point scale, where 7=not at all limited and 1=totally limited.

The 32 questions (items) are assigned as follows to the 4 domains:

Symptoms: Items 6, 8, 10, 12, 14, 16, 18, 20, 22, 24, 29, 30

Activity limitation: Items 1, 2, 3, 4, 5, 11, 19, 25, 28, 31, 32

Emotional function: Items 7, 13, 15, 21, 27

Environmental stimuli: Items 9, 17, 23, 26

Individual items are equally weighted. The overall score of the AQLQ(S)+12 will be derived as the average of the 32 items; thus, the overall score ranges from 1 ("total impairment") to 7 ("no impairment"). The domains are summarized in exactly the same way – each domain score will be derived as the average score of the items for the specific domain. Each domain score thus also ranges from 1 ("total impairment") to 7 ("no impairment").

The aim is not to have any missing data on the questionnaire. The data for a completed questionnaire will not be used (ie, will be set to missing) in the following cases:

- For calculation of overall score: if > 3 missing responses in total or > 1 missing response in any domain
- For calculation of symptom or activity limitation domain scores: if > 1 missing response in the domain, or
- For calculation of emotional function and environmental stimuli domain scores: if any missing response in the domain.

In case the number of missing values does not exceed the specifications listed above, imputation of missing values will be performed using the same method as described for the ACQ questionnaire in [Section 6.2.4](#) [5].

Imputed values will be flagged in subject listings.

6.2.6 Asthma Symptom Diary

For the data collected by subjects in their diaries, if any data are recorded after the subject end of study date, this will not be used for any of the presentations described in this SAP; ie, only diary data collected up to the earlier of the end of study date or the diary deactivation date will be used for study data analysis.

6.2.6.1 Symptom Scores

The ASD is a 6item daily measure of asthma symptom severity that assesses 3 core categories of asthma symptoms: breathing symptoms (difficulty breathing; wheezing; shortness of breath), chest symptoms (chest tightness; chest pain), and cough. The ASD is intended for twice daily completion and comprises a morning diary (for completion upon waking and referring to asthma symptoms during the nighttime) and an evening diary (for completion before going to bed and referring to asthma symptoms during the day).

Subjects are required to rate the 6 symptoms at their worst during the respective timeframes using an 11-point numeric rating scale ranging from 0 ('None') to 10 ('As bad as you can imagine') [6].

Individual morning and evening ASD symptom scores for the 6 symptoms of difficulty breathing, wheezing, shortness of breath, chest tightness, chest pain, cough will be reported for each symptom as recorded in the diary. If the assessment of a particular symptom is missing for either the morning or evening diary, then that symptom's score for that diary timepoint will be missing.

Mean symptom scores will be calculated for each symptom as the mean of the available scores for the applicable symptom for each week, as follows:

$$\frac{\text{sum of available entries for the week, for each symptom}}{\text{number of available entries for the week, for each symptom}}$$

A mean ASD score will be calculated as the mean of all available symptom scores for each week, as follows:

$$\frac{\text{sum of available entries for the week, for all symptoms}}{\text{number of available entries for the week, for all symptoms}}$$

The first week post-baseline will start with the morning diary on Day 1 and will end with the evening diary 1 week later on Day 7 (ie, if there are no missing entries, a week will comprise 14 entries for each symptom). If Day 1 entries are utilized to calculate a baseline value (see [Section 9.2](#)), these Day 1 entries will not be part of the first week post-baseline (ie, in this case the first week post-baseline will start with the morning diary on Day 2 and will end with the evening diary on Day 7). For the mean symptom scores, if a subject has > 3 missing morning diary entries or > 3 missing evening diary entries for the applicable symptom in a week, then the mean symptom score for that week will be missing. For the mean ASD score, if a subject has > 3 missing morning diary entries or > 3 missing evening diary entries for any of the 6 symptoms

in a week, then the mean ASD score for that week will be missing. Mean scores for all subsequent weeks will be defined similarly, with the same rule for handling missing data. Baseline is defined in [Section 9.2](#).

6.2.6.2 Additional Endpoints from Diary Data

A peak flow meter measures how well the lungs are able to expel air. Subjects will measure peak flow daily on a device provided by the sponsor and record the results in their diary. The daily peak flow rate as well as the use of SABA, which will also be recorded in the diary, will be used to assess the occurrence of asthma related events (see [Section 6.2.1](#)).

Peak flow rate is recorded daily by the subject. Mean peak flow rate will be calculated as the mean of all available recordings for each week, as follows:

$$\frac{\text{sum of available entries for the week}}{\text{number of available entries for the week}}$$

The first week post-baseline will start with the recording in the diary on Day 1 and will end with the recording in the diary on Day 7 (ie, if there are no missing entries, a week will comprise 7 entries). If the Day 1 entry is utilized as baseline (see [Section 9.2](#), Definition 1 for mean peak flow rate), the Day 1 entry will not be part of the first week post-baseline (ie, in this case the first week post-baseline will start with the Day 2 diary recording and will end with the Day 7 diary recording). If a subject has > 3 missing entries in a week, then the mean score for that week will be missing. Mean values for all subsequent weeks will be defined similarly, with the same rule for handling missing entries. Baseline is defined in [Section 9.2](#) (Definition 1 for mean peak flow rate).

The number of times (number of puffs/inhalations) a SABA is used will be assessed by reviewing the diary maintained by the subject. The number of puffs/inhalations of SABA is entered by the subject in their diary twice daily, ie, the morning diary is used to record number of SABA puffs/inhalations during the nighttime and the evening diary is used to record number of SABA puffs/inhalations during the day. For analysis of the SABA use data, beginning with the day on which the diary is activated through the earlier of the end of study date or the diary deactivation date, all missing entries will be considered 0 for analysis. Daily sums of SABA puffs/inhalations will be calculated as the sum of the morning diary and evening diary entries for the same calendar date. Mean daily number of puffs/inhalations over weekly periods will be calculated from the daily sums, as follows:

$$\frac{\text{sum of daily sums for the week}}{\text{number of days the diary was available for the week}}$$

For the first mean daily number of puffs/inhalations post-baseline, the week will start with the morning diary on Day 1 and will end with the evening diary 1 week later on Day 7 (ie, a week will comprise 14 entries). If Day 1 entries are utilized as baseline (see [Section 9.2](#), Definition 1 for mean daily number of SABA puffs/inhalations), the Day 1 entries will not be part of the first week post-baseline (ie, in this case the first week post-baseline will start with the morning diary on Day 2 and will end with the evening diary on Day 7). Mean daily number of SABA

puffs/inhalations for all subsequent weeks will be defined similarly, with the same rule for handling missing entries. Baseline is defined in [Section 9.2](#) (Definition 1 for mean daily number of SABA puffs/inhalations).

6.2.7 European Quality of Life – 5 Dimension 5 Level Questionnaire

The EQ-5D-5L consists of the EQ-5D descriptive system and the EQ VAS. The descriptive system includes 5 dimensions: mobility, self-care, usual activities, pain/discomfort, and anxiety/depression. Each dimension has 5 levels: no problems, slight problems, moderate problems, severe problems, and extreme problems. The EQ VAS records the subject's self-rated health on a vertical VAS, where the endpoints are labelled 'The best health you can imagine' (100) and 'The worst health you can imagine' (0) [7].

6.2.8 Patient Global Impression of Change/Severity

The PGI-C/S scale is a global index that can be used to rate the severity of a specific condition (a single-state scale) from the patient's perspective.

The PGI-S for this study is a single question asking the subject to rate the current state of their overall asthma severity on a 7-point scale (normal, borderline, mild, moderate, marked, severe, extreme). The PGI-C for this study is a single question asking the subject to rate their overall asthma status since the start of the study, (ie, since baseline [Visit 2]) on a 7-point scale (very much improved, much improved, minimally improved, no change, minimally worse, much worse, very much worse).

